All study investigators will have access to research records and data. Hard copy research data/records will be coded, no individual will be identified by name, and the data will be stored in a locked filing cabinet locked to protect subject anonymity. Electronic data with identifiers (including neuroimaging) will be saved password-protected NIH-issued computers on secured servers. Neuroimaging data will be maintained on a secure internet-based server. Only study investigators will have access to the data. De-identified results from clinical trials will be posted on clinicaltrials.gov.

Clinical data will be managed according to NIH Clinical Center's standard policies (<http://www.cc.nih.gov/participate/patientinfo/legal.shtml>). Sensitive, private information (such as a urine drug test) will not be collected in this study, so no special protections for NIH employees and staff are necessary. However, confidentiality protections for them will be the same as those for all subjects. The PI will instruct all study personnel in the relevant SOPS and procedures to ensure the privacy of NIH employees and staff who participate in our study. All investigators will be required to read the SOP on participation of NIH personnel.

Participant research data will be de-identified and stored on secure computer systems. The only entries in the medical record will be to document participation in the research study. In laboratory records, all personally-identifying information will be removed. Participants will be identified by a number code, the key to which will be accessible only to the investigators. The information gathered during this study will be kept confidential to the extent that the law allows. The lab results will be kept safe in a locked room. The subjects will be informed that these results may be published for scientific purposes, provided their identity is not revealed.

Members of the CNRM, Uniformed Services University, Henry M Jackson Foundation, US Department of Defense and NIH, may have access to the study data for auditing purposes.

b. For medical records

Clinical data will be managed according to NIH's Clinical Center's policy (<http://www.cc.nih.gov/participate/patientinfo/legal.shtml>).

20. Conflict of Interest

a. Distribution of NIH Guidelines

NIH guidelines on conflict of interest have been distributed to all investigators.

b. Conflict of Interests

There are no conflicts-of-interest to report.

c. Role of a Commercial Company or Sponsor

There is no commercial company or sponsor.

21. Technology Transfer

N/A

22. Research and Travel Compensation

All participants will be compensated for time and research-related inconveniences in accord with NIH guidelines as follows:

Experiment 1	Number	Pay per Procedure	Total
Time for first hour	2-7	\$20	40-160
Time for each additional hour	1-3	\$10	30
rTMS	1-5	\$60	60-300
MRI	2	\$60	120
Urine pregnancy test	2-6	\$10	20-60
Experiments 1 Total			\$250-650
Experiment 2			
Time for first hour	3-8	\$20	80-160
Time for each additional hour	6-11	\$10	60
rTMS	1-5	\$60	60-300
MRI	2	\$60	120
Behavioral Tasks	3	\$30	90
Urine pregnancy test	2-6	\$10	20
Experiment 2 Total			\$250-840

Payment (check) will be mailed to participants after they complete the protocol. If participants are unable to finish the study, they will be paid for the portion of the study completed. No reimbursement for travel or escort fee will be provided.

Employees and staff who participate during work hours must have permission from their supervisor. NIH employees must either participate outside of work hours or take leave in order to receive compensation

24. References

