
may have saved time, reliable biomarkers could have been helpful by providing surrogate endpoints and better mechanistic understanding. The absence of biomarkers or similar surrogate endpoints has also made the dosing parameter space difficult to explore efficiently, since this would have to rely on behavioral endpoints in most cases. In this context, it is notable that, despite intensive research, the field has delivered only one widely adopted use whose several delivery parameters have never been optimized. Biomarkers of target engagement or surrogate endpoints with less variability than behavioral outcomes might have avoided some of the blind alleys.

Wang et al. (2014) have provided a paradigm, which may prove useful in solving these and other problems for noninvasive brain stimulation in the clinical domain. As a way to target the hippocampus, a deep structure beyond the reach of TMS, they used a conventional functional magnetic resonance imaging (fMRI) measurement, functional connectivity (FC), to find an individually customized, upstream cortical target, connected by a known monosynaptic pathway from the parietal cortex to the hippocampus. By individualizing the stimulation site using fMRI, Wang and colleagues eliminated the effect of inter-individual differences in anatomy, which can impact the results of a stimulation intervention (Karabanov, Chao, Paine, & Hallett, 2012). By applying rTMS repeatedly to this target, they caused an increase in memory performance and a correlated change in FC between the stimulated area and the area of interest deep in the brain. Incidentally, rTMS also caused dramatically increased connectivity in a network of sites related to visual memory and outside the stimulated pathway. Their work suggested that FC could be used as a marker of target engagement for noninvasive brain stimulation studies and, possibly, as an endpoint in clinical trials.

This protocol is an attempt to use FC as an endpoint, first in a dose finding study aimed at determining the number of rTMS sessions required to produce a meaningful degree of modulation in the pathway studied by Wang et al., then in an experiment involving a different pathway, and finally in a clinical trial in amnestic TBI patients.

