2. Study Objectives and hypotheses

The overall objective of this study is to determine whether functional connectivity can be used as a biomarker of rTMS synaptic modulation. The experiments outlined in this protocol will not be used to demonstrate the clinical effects of rTMS.

a. Aims

Experiment 1

Specific Aim 1: To determine the number of rTMS sessions required to produce a substantial change in FC between the parietal cortex and hippocampus in healthy subjects.

Experiment 2

Specific Aim 2: To determine whether rTMS delivered to the parietal cortex increases parietal-hippocampal FC in healthy subjects.

Specific Aim 3: To measure the effect of parietal rTMS on AMT and WPT-I, performance.

Specific Aim 4: To evaluate the relationship between fMRI connectivity and AMT and WPT-I outcomes after parietal rTMS in healthy subjects.

b. Hypotheses

i. Primary Hypotheses

Experiment 2: rTMS of the left parietal cortex will increase FC between the left parietal cortex and the hippocampus compared to rTMS of the vertex. rTMS of the left parietal cortex will significantly increase explicit memory compared to rTMS of the vertex.

ii. Secondary hypotheses:

Experiment 2: rTMS of the left parietal cortex will decrease FC between the left caudate (head) and parietal cortex compared to rTMS of the vertex. rTMS of the left parietal cortex will significantly decrease implicit memory compared to rTMS of the vertex.

3. Subjects

a. Description of study populations

We will study 50 healthy individuals (Experiment 1: 18; Experiment 2: 32). We are requesting up to 101 healthy volunteers as the accrual ceiling to account for dropouts and screening failures.

b. Inclusion criteria

Healthy individuals in Experiments 1 and 2.

- Age 18-50 (inclusive)
- English speaking and writing

c. Exclusion criteria

- Any current major neurological or psychiatric disorder such as (but not limited to) stroke, Parkinson disease, Alzheimer disease, schizophrenia or major depression
- History of seizure
- Medications acting on the central nervous system
- Ferromagnetic metal in the cranial cavity or eye, implanted neural stimulator, cochlear implant, or ocular foreign body
- Implanted cardiac pacemaker or auto-defibrillator or pump
- Non-removable body piercing
- Claustrophobia
- Inability to lie supine for 1 hour
- Pregnancy, nursing, or plans to become pregnant during the study.
- Members of the NINDS Behavioral Neurology Unit (BNU)
- For Experiment 2: Participation in Experiment 1

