We will use the continual reassessment method (CRM) design (O’Quigley et al., 1990) to find the optimal number of sessions to produce a clinically meaningful change in fMRI connectivity between the parietal cortex and hippocampus in healthy subjects. The CRM is an adaptive design for dose finding studies, in which a “dose-toxicity” curve is fitted to the data and each patient will be assigned the dose most likely to be associated with the target toxicity level, designated as maximum tolerated dose (MTD) (Garrett-Mayer, 2006). It is important to note that while we retain the toxicity terminology from the CRM literature in the following description, we have adapted the technique to finding the threshold for efficacy, not toxicity.

In our study, the escalation decisions will be based on the efficacy of the rTMS. For the purpose of this study, the term dose will be used to mean the number of rTMS sessions. Similarly, the term toxicity will correspond to efficacy of the rTMS.

First, we used the data by Wang et al. (2014) to determine the threshold value for a clinically meaningful change in connectivity. The optimal cut-point for dichotomizing FC change was 0.028, which was determined by maximizing the Youden’s index (sensitivity+specificity1) in the ROC analysis.

The details and assumptions to implement CRM are as follows.

- **Dose limiting toxicity (DLT):** We assume that a FC change equal to or greater than the threshold value 0.028 is an effective change. DLT will be defined as the FC change from baseline to post-stimulation ≥ 0.028
- **Target toxicity level (TTL):** The sensitivity for the dichotomized FC change (at 0.028) in the parietal stimulation group was 87.50% in Wang et al. (2014). TTL is set to 12.5%, which is equal to (1-sensitivity). *The MTD is then defined as the number of rTMS sessions that has a risk of DLT equal to the chosen TTL value of 12.5%.*
- **Dose levels:** The dose level refers to the number of consecutive rTMS sessions.

The range of sessions is 1 to 5.

- **Number of healthy volunteers per dose level:** 3 healthy volunteers per dose level
- **Dose-toxicity model:** We propose to use a one-parameter hyperbolic-tangent dose-response model by O'Quigley et al. (1990), where a Gamma (1, 1) prior will be used.
- **Starting dose:** 3 sessions
- **Stopping rule:** Healthy volunteers will continue to be recruited to the trial until a fixed sample size of 15 is achieved.

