The following aims will be investigated using the optimal sessions determined in Specific Aim 1.

ii. Experiment 2

Specific Aim 2 (Primary Aim 1): To determine whether rTMS delivered to the parietal cortex increases parietal-hippocampal FC in healthy subjects.

For each healthy subject, the Pearson correlation coefficients (r) between time courses of BOLD activity in the parietal and hippocampal areas will be calculated to determine the functional connectivity before and after rTMS stimulation. They will be Fisher-transformed to normalize r values. *We will call this the z scores.* The change in the z scores from pre- to post- stimulation will be assessed using the one-tailed, paired *t* test.

Specific Aim 3: To measure the effects of parietal rTMS on AMT and WPT-I.

First, the change in the AMT scores from pre- to post- stimulation will be calculated. Then, the two sample *t*-tests will be used to compare the changes in the AMT scores between the parietal and the sham groups. Additionally, we will consider using the Wilcoxon rank sum tests when the changes in the AMT scores are not normally distributed in each group.

Next, we will perform a similar analysis for WPT-I scores.

Specific Aim 4: To evaluate the relationship between fMRI connectivity and AMT and WPT-I outcomes in the parietal group in healthy subjects.

For each subject, the Pearson correlation coefficients (r) between time courses of the parietal and hippocampal regions will be calculated to determine the functional connectivity before and after rTMS stimulation. Then, the changes of the z scores (Fisher transformed r values) from pre- to post- simulation will be calculated. Similarly, the changes in AMT scores from pre- to post-simulation will be computed. The linear

regression models will be used to examine the relationship between the change in functional connectivity and the change in AMT scores.

Next, we will repeat a similar analysis using WPT-I scores.

b. Power analysis

Experiment 1: The maximum number of healthy subjects for Experiment 1 is set at 15.

Experiment 2: We propose to recruit 32 healthy participants (16 subjects in each of the parietal and control groups) to participate in Experiment 2.

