We based our sample size estimate on the behavioral results from the study we are replicating (Wang et al., 2014). In Wang et al. (2014), the effect size of the memory increases caused by PPC stimulation, compared to sham stimulation, was 0.75 (Cohen's d). This was achieved using a within-subjects design. Using this effect size, to achieve a β of 0.70 using the between subjects design described in this protocol (Experiment 2), 16 participants are required.

Sixteen subjects per group also achieves sufficient power to detect FC changes. Wang et al. indicate that the mean difference in FC from post to pre stimulation in retrosplenial region was 0.1018 and its standard deviation was 0.09296. Based on their data, we assume that the mean change will be between 0.1008 and 0.1028. We also assumed its standard deviation (SD) will be between 0.085 and 0.10. A one-tailed, paired t-test was used at a significance level of 0.05. Computations were carried out using PASS (Hinze J. [2008] PASS, NCSS, LLC, Kaysville, Utah).

The following table shows estimates of power to address Primary Aim 1 given ten subjects per treatment group.

Mean of paired difference	Estimated standard deviation of the difference	Power
0.1008	0.085	0.96440
0.1018	0.085	0.96698
0.1028	0.085	0.96940
0.1008	0.093	0.93446
0.1018	0.093	0.93833

0.1028	0.093	0.94202
0.1008	0.100	0.90159
0.1018	0.100	0.90651
0.1028	0.100	0.91125

Table 1. Estimated power for primary aim 1 (N=10 in parietal group)

A sample size of ten subjects per group achieves 93.8% power to detect a mean of paired differences of 0.1018 with an estimated standard deviation of differences of 0.093 and with a significance level of 5% using a one-sided paired t-test. Under other scenarios, the estimated powers were greater than 90%.

Assuming a 50% dropout rate, we anticipate enrolling up to 101 healthy subjects (33 for Experiment 1; 64 for Experiment 2).

11. Human Subjects Protection

a. Subject selection

We will recruit healthy participants through referrals from the NIH Clinical Research Volunteer program or through self-referrals to the protocol. We will work to ensure equitable selection.

b. Justification for exclusion of subjects

i. Justification for exclusion of children

Children will not be included. The study is predicated on the work of Wang et al. (2014) who studied participants over the age of 18. Therefore, in order to replicate this result, we will recruit a sample of the same age.

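### The primary FC hypothesis and the biomarker objective need parietal separated from vertex stimulation, but the only planned FC effect test in Experiment 2 is a paired test with no vertex term

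*Combined protocol and SAP*

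**What the plan says.** Section 2 (Study Objectives and hypotheses) states: "The overall objective of this study is to determine whether functional connectivity can be used as a biomarker of rTMS synaptic modulation". The primary FC hypothesis for Experiment 2, in section 2.b.i, is comparative: "rTMS of the left parietal cortex will increase FC between the left parietal cortex and the hippocampus compared to rTMS of the vertex". Section 1.d gives the reason for the vertex group: to control for sensory and other nonspecific effects of the stimulation.

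Section 10.a.ii, Specific Aim 2 (Primary Aim 1), gives the analysis: "The change in the z scores from pre- to post- stimulation will be assessed using the one-tailed, paired" t test. No vertex term appears. The power calculation in section 10.b follows the same route: "A one-tailed, paired t-test was used at a significance level of 0.05". The title of Table 1 refers to the parietal group alone. For memory (Aim 3), by contrast, the plan compares change between the two groups with a two-sample test. Aim 4 uses individual FC changes, but only in regressions with memory change within the parietal group.

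Experiment 1 scores each participant against an FC change of 0.028, a cut-point that maximised Youden's index in the source study's data. Section 10.a.i reports its performance there: "The sensitivity for the dichotomized FC change (at 0.028) in the parietal stimulation group was 87.50" per cent. No specificity is given, and the cut-point is not used in Experiment 2. Section 1.a explains why the answer matters, saying of the source study that its results suggested "FC could be used as a marker of target engagement for noninvasive brain stimulation studies and, possibly, as an endpoint in clinical trials".

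**The concern.** A pre-post change in one group mixes the effect of the target with everything else that can move FC between two scans: repeat scanning, time, the sensation of stimulation and nonspecific neural effects. The vertex group was included to remove those components, but the FC test as written does not use it. A positive result would therefore not establish the stated hypothesis, and it would be weak support for calling FC a marker of parietal stimulation.

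Two further gaps bear on the biomarker conclusion. First, nothing in Experiment 2 estimates how far FC change separates the two groups, although both are scanned in the same way. Second, the outcomes in section 9 are FC, memory scores and correlations with white matter integrity. Synaptic modulation is not measured independently of FC, so no planned analysis can show that FC tracks it.

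**Working it through.** **Inputs.** From section 10.b: 16 per group; planning mean change 0.1018; SD 0.093 (source value 0.09296, range considered 0.085 to 0.10), given for the retrosplenial region; one-sided alpha 0.05. From section 10.a.i: cut-point 0.028. The documents give no vertex mean or SD. I assume normal changes, the same SD in both groups and, except where stated, a vertex mean of 0. I also assume that the retrosplenial SD and the 0.028 cut-point apply on one scale to the parietal-hippocampal outcome; the documents do not say so.

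**1. The plan's own figure.** Paired-t power = P(T > t(0.95, n−1)), with T noncentral t on n−1 df and noncentrality (mean/SD)·√n. For n = 10, mean 0.1018 and SD 0.093 this gives 0.93833, as in Table 1. All nine entries reproduce. At the planned n = 16 the power is 0.994 (0.998 at SD 0.085, 0.987 at SD 0.10).

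**2. Smallest observed change that passes.** t(0.95, 15)/√16 = 1.753/4 = 0.438 SD. At SD 0.093 this is 0.0408 (0.0373 to 0.0438 over the SD range), and 0.0408/0.1018 = 40% of the planned effect.

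**3. Separation at that point, vertex mean 0.**
- AUC = Φ(d/√2) = Φ(0.438/√2) = 0.62.
- Parietal participants at or above 0.028: Φ((0.0408 − 0.028)/0.093) = 55%.
- Vertex participants at or above 0.028: 1 − Φ(0.028/0.093) = 38%.
- Over SD 0.085 to 0.10 the two percentages run 54–56% and 37–39%.

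**4. Equal true change in both groups (AUC 0.50).** The paired test passes with the power it has at that change, from the formula in step 1 with n = 16 and SD 0.093:
- true change 0.0408: 0.51
- true change 0.06: 0.79
- true change 0.1018: 0.99

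**5. Separation at the planned effect, vertex mean 0.** d = 0.1018/0.093 = 1.09, so AUC = 0.78 (0.76 to 0.80 over the SD range). At 0.028, sensitivity is Φ((0.1018 − 0.028)/0.093) = 79%, with 38% of vertex participants positive. The Hanley–McNeil standard error of an AUC of 0.78 with 16 versus 16 is 0.083, giving an approximate 95% CI of 0.78 ± 1.96 × 0.083 = 0.62 to 0.94.

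**6. A two-sample test instead.** Noncentrality d·√(16/2), 30 df. At SD 0.093 the power is 0.916 one-sided or 0.850 two-sided. Over SD 0.085 to 0.10 it runs 0.952 to 0.879 one-sided and 0.906 to 0.796 two-sided. Such a test is just significant at d = t·√(2/16): 0.600 one-sided (AUC 0.66) or 0.722 two-sided (AUC 0.70).

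**The case against.** The strongest reply is that a response marker need not classify individuals. Section 1.a presents FC as evidence of target engagement and a possible endpoint, something that moves when the pathway is stimulated. The primary hypothesis is about groups, and a mean contrast is a legitimate way to test it. This stands. A reader might infer that the biomarker objective fails unless FC change can identify who was stimulated, or that an AUC threshold should decide it. The documents set no such requirement. A rule that the lower AUC limit exceed 0.5 would also add little: with 16 versus 16 it is met at an AUC of about 0.69, almost where a two-sided two-sample t test becomes significant (0.695).

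It is also fair that 0.041 is the edge of significance and not the expected result. At the planning values a boundary result is unlikely, and separation with vertex at zero would be moderate (AUC 0.78). That does not answer the equal-change case, in which larger nonspecific effects make the paired test more likely to pass.

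A reader might further infer that the 87.5% sensitivity will never meet new data. Experiment 1 does score up to 15 new parietal participants at 0.028. What it cannot supply is specificity, because it has no control group. Nor would a different sensitivity in Experiment 2 by itself show that the source figure was optimistic, since the number of sessions may differ from the five given in the source study.

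Finally, no section says that a significant paired test alone establishes the biomarker. True, but no section says what would.

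**Conclusion.** The point holds as a mismatch between hypothesis and test. The FC hypothesis is parietal versus vertex; the written test is parietal before versus after. It can pass at 40% of the planned change, with an AUC of about 0.62 if vertex change is zero. It passes with probability 0.51 to 0.99 for true changes of 0.041 to 0.1018 when the groups do not differ at all. The equal-change probabilities rest on normality and the SD of 0.093. The AUC and cut-point figures also need the equal-SD and zero-vertex assumptions, and the cut-point figures a common scale. The mismatch itself rests on the text alone.

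The documents do not support the stronger conclusion that the plan must show individual classification. The biomarker conclusion should rest on the between-group contrast, with measures of separation reported beside it so that a significant but modest difference is seen for what it is.

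**What to change.** In section 10.a.ii, Aim 2:

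- Make the primary FC analysis a two-sample comparison of Fisher-z change, parietal versus vertex, with the sidedness fixed in advance. The within-group paired test can stay as a secondary description.
- State in section 2 that the biomarker conclusion rests on this contrast and not on the within-group p-value.
- As supporting estimates, report the AUC of FC change for parietal versus vertex with a 95% CI, and the sensitivity and specificity of the fixed 0.028 cut-point with exact 95% CIs. Read the sensitivity in light of the number of sessions given.
- Word the conclusion as a marker of response to parietal rTMS, since synaptic modulation is not measured independently.
- In section 10.b, replace Table 1 with power for the two-sample test at 16 per group, and state the assumed vertex change and the region from which the SD comes.

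The cost is some text and no new data, settled before FC results are seen by group. FC power under the planning values falls from 0.994 (paired, n = 16) to about 0.92 one-sided or 0.85 two-sided. The supporting intervals will be wide: about 0.62 to 0.94 for the AUC at the planned effect and, as an example, 62% to 98% for a sensitivity of 14/16.
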